1. SCIENTIFIC BACKGROUND

Initial joint alignment in closed kinetic chain resistance exercises is a determinant factor for load transfer and inter-segmental force transmission (Neumann, 2019; Straub and Powers, 2024). Among these exercises, the leg press is widely used in strength and hypertrophy-oriented programs owing to its capacity to accommodate high mechanical loads while providing external support for trunk stability (Martín-Fuentes et al., 2020). Foot placement on the platform during leg press constitutes an important initial condition that may influence force transmission and joint loading patterns along the lower extremity (Da Silva et al., 2008). Given the natural inter-individual variability in the rotational alignment of the lower extremity, whether standardized foot positions applied during leg press generate equivalent biomechanical conditions across individuals represents an important consideration for the development of individualized training strategies.

One of the key indicators that quantifies these natural rotational differences is the foot progression angle (FPA). The FPA is an important biomechanical parameter that defines the angular relationship between the longitudinal axis of the foot and the direction of progression during gait, reflecting the rotational alignment of the lower extremity in the transverse plane (Caderby et al., 2022; Cibulka et al., 2016). This angle, which may vary among individuals, is regarded not only as a descriptive feature of gait pattern but also as a functional indicator of habitual lower extremity alignment (Caderby et al., 2022; Shen et al., 2026). It has been reported that inter-individual differences in FPA may be associated with tibial rotation and load distribution at the knee joint (Bennour et al., 2017; Cibulka et al., 2016; Qiu et al., 2020), and may also alter lower extremity muscle activation (Rutherford et al., 2010).

The effects of foot placement on lower extremity biomechanics during leg press exercise have been examined in the literature through various manipulations. These studies have focused on the effects of variables such as foot height on the platform, foot width, or fixed internal–external rotation angles on muscle activation and joint loading (Da Silva et al., 2008; Escamilla et al., 2001; Harandi et al., 2013; Martín-Fuentes et al., 2020; Martín-Fuentes et al., 2022; Pereira et al., 2017). However, in these studies, standardized foot positions were applied to all participants and rotational manipulations were performed using fixed angles. The absence of FPA from the initial foot positioning suggests that these studies operated under the assumption that applied foot positions generate similar biomechanical conditions across all individuals.

Furthermore, biomechanical differences associated with foot position in previous research have predominantly been assessed through electromyographic muscle activation and kinematic parameters (Martín-Fuentes et al., 2020; Da Silva et al., 2008; Martín-Fuentes et al., 2022). While electromyography provides information on the neural dimension of muscle activation (Disselhorst-Klug, 2025), tensiomyography enables assessment of contractile properties through the mechanical response of the muscle to electrical stimulation and can provide important information regarding the functional state of the muscle (Rey et al., 2012; Fernández-Baeza et al., 2024). The absence of tensiomyographic methods in the aforementioned studies limits the direct assessment of the effects of initial foot positioning on skeletal muscle contractile properties.

In this context, the existing literature presents a clear gap with respect to both the integration of individual rotational alignment differences (FPA) into exercise starting position and the evaluation of this interaction through muscle contractile properties.

2. STUDY OBJECTIVES AND HYPOTHESES

2.1. Primary Objective

To examine the effects of the interaction between rotational foot positioning during leg press exercise and individuals' habitual foot progression angle (FPA) phenotype on the acute contractile response of the vastus medialis muscle.

2.2. Hypotheses

Primary hypothesis: When the foot rotation position applied during exercise is incongruent with the individual's habitual foot progression angle, the contractile responses of the vastus medialis muscle would be more pronounced.

Secondary hypothesis: A neutral foot position in individuals with a habitually high FPA profile, and an externally rotated foot position in individuals with a normal FPA profile, would be associated with greater contractile responses.

3. STUDY DESIGN

This study was designed as a mixed-design, crossover experimental investigation. In the study design, FPA phenotype (high FPA vs. normal FPA) was defined as the between-subjects factor, while foot rotation protocol (0° neutral vs. 30° toe-out) and time (pre-exercise vs. post-exercise) were defined as within-subjects factors.

All participants were assessed in two separate sessions, each involving one of the two foot rotation protocols, with a 48-hour washout period applied between sessions to minimize potential fatigue and carry-over effects. Within the crossover design, protocol order was fixed on a group-specific basis to minimize learning effects. Accordingly, each group performed the condition congruent with their habitual foot progression angle in the first session and the incongruent condition in the second session.

Pre-exercise TMG values obtained prior to the second session were compared with baseline measurements to confirm return to baseline levels. All experimental procedures were conducted under controlled environmental conditions (24°C) and within the same time-of-day window for each participant (± 1 hour). Participants were instructed to avoid strenuous physical activity and caffeine consumption for 48 hours prior to each measurement.

To minimize measurement bias, the researcher conducting TMG assessments was blinded to participants' phenotype group and the exercise condition applied (single-blind). Exercise administration and data analysis were performed by different researchers, and group codes were anonymized during the analysis process.

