6. STATISTICAL CONSIDERATIONS

Statistical analyses were performed using SPSS software (Version 27, IBM Corp., Armonk, NY, USA). Descriptive statistics are presented as mean \pm standard deviation (mean \pm SD) and the significance level was set at $\alpha = 0.05$. Normality of continuous variables was assessed using the Shapiro–Wilk test and homogeneity of variance was evaluated with Levene’s test.

To assess potential carry-over effects associated with the crossover design, pre-exercise measurements obtained prior to the second session were compared using paired samples t-tests within each group; no significant carry-over effect was observed (all $p > 0.05$).

A 2 (Group: HFPA vs. NFPA) \times 2 (Protocol: congruent vs. incongruent) \times 2 (Time: pre vs. post) factorial repeated measures ANOVA were applied to examine changes in muscle contractile parameters. Group was included as a between-subjects factor, while protocol and time were included as within-subjects factors. Main effects and all two-way (Group \times Protocol, Group \times Time, Protocol \times Time) and three-way (Group \times Protocol \times Time) interactions were evaluated. As each within-subject factor had two levels, the sphericity assumption was automatically satisfied and no correction was applied.

Primary outcome variables were defined a priori as Dm and Tc. In line with the primary hypothesis of the study, the Protocol \times Time interaction was prioritized during analysis and interpretation.

Where significant main effects or interactions were identified, pairwise comparisons were conducted with Bonferroni correction. Additionally, 95% confidence intervals for mean differences were calculated and reported for all post-hoc comparisons.

Effect sizes were reported as partial eta squared (η^2) and interpreted as small (0.01), medium (0.06), and large (0.14) (Richardson, 2011). The Td parameter was treated as a secondary outcome variable and only significant effects are reported.

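### The congruent condition always comes first, so the prioritised Protocol × Time contrast cannot be separated from a session effect on the pre-to-post response

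*Protocol*

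**What the plan says.** Protocol section 3 calls the study a mixed-design crossover with two sessions, "with a 48-hour washout period applied between sessions to minimize potential fatigue and carry-over effects". It gives one order of conditions for everyone: "each group performed the condition congruent with their habitual foot progression angle in the first session and the incongruent condition in the second session". The reason offered is that "protocol order was fixed on a group-specific basis to minimize learning effects".

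The primary hypothesis (section 2.2) is that when the foot position is "incongruent with the individual's habitual foot progression angle, the contractile responses of the vastus medialis muscle would be more pronounced". Section 6 sets the within-subject factor as "Protocol: congruent vs. incongruent", alongside Group and Time, and says of Protocol × Time that this "interaction was prioritized during analysis and interpretation". Section 5.7 gives the same priority for Dm and Tc.

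The only check on session differences is in sections 3 and 6: resting values before session 2 are compared with baseline by paired t-tests within each group, and no significant difference is reported. No session or period term is specified.

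**The concern.** A crossover separates condition from session only if some participants take the conditions in each order. Here nobody takes the incongruent condition first. A response that differs between the first and second bout for any reason tied to order would look exactly like the hypothesised congruence effect, or would mask it if it ran the other way.

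The stated reason for the fixed order works against the design. A fixed order does not reduce learning effects. Whatever learning affects the response falls wholly on one side of the comparison, and only counterbalancing would spread it evenly.

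At stake is the interpretation of the prioritised test for both primary outcomes, and of the section 2.1 objective and the section 2.2 secondary hypothesis, which rest on the same comparison.

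**Working it through.** **Step 1: conditions by session.** Foot angles follow from sections 2.2 and 3.

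| Group | Session 1 (congruent) | Session 2 (incongruent) |
|---|---|---|
| HFPA, n = 12 | 30° | 0° |
| NFPA, n = 12 | 0° | 30° |

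Both positions that the secondary hypothesis expects to give greater responses (neutral in HFPA, external rotation in NFPA) fall in session 2.

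**Step 2: aliasing.** Code Group, Session and Time as ±1 over the eight cells.

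- Congruence equals Session in every cell, so Congruence × Time equals Session × Time (correlation 1).
- Foot angle equals Group × Session up to sign. Group × Angle × Time, the interaction in the primary objective, is therefore also Session × Time.
- Adding Session and Session × Time to the eight-parameter ANOVA gives 10 columns, but the rank stays at 8. Neither can be estimated.
- In section 6's coding, Group × Protocol × Time is foot-angle × time. Its inner product with Session × Time over the eight cells is 0. The same holds for Group × Time.

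Section 3 describes the factor as 0° versus 30° and section 6 as congruent versus incongruent. The choice does not help: under either coding, the term that carries congruence is the one aliased with session.

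**Step 3: what is confounded.** For each participant let D = (post − pre) in session 2 minus (post − pre) in session 1. The Protocol × Time test asks whether the mean of D is zero. A constant added to both pre and post in session 2 drops out of D. A session effect δ on the pre-to-post change goes into D in full.

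**Step 4: illustrative size.** The plan has no figure for a session effect to reproduce, so δ is an assumption. Inputs from the documents are N = 24 in two groups (error df 22), α = 0.05 and r = 0.50 (section 4.5). I also assume equal variances and a common correlation among the four measurements.

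- SD(D) = √[4(1 − r)] = √[4 × 0.50] = 1.414 raw SD
- SE = 1.414 / √24 = 0.289 raw SD
- Noncentrality λ = (δ / SE)², referred to noncentral F(1, 22)

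Chance of a significant primary test when congruence has no effect:

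| δ (raw SD) | δ / SE | Chance |
|---|---|---|
| 0 | 0 | 5% |
| 0.1 | 0.35 | 6% |
| 0.3 | 1.04 | 17% |
| 0.5 | 1.73 | 38% |

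The rates rise with r. If the test–retest ICC for Tc (0.88, section 5.3) is taken as the common correlation, SD(D) = √[4 × 0.12] = 0.693 and SE = 0.141. Then δ = 0.1 gives about 10% and δ = 0.3 about 53%.

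**Step 5: the carry-over check.** It compares resting values, whereas D concerns the response to exercise. Resting values can return to baseline while the response still differs. With n = 12, a paired t-test also has power of only 16%, 35% and 71% for baseline shifts of 0.3, 0.5 and 0.8 SD of the paired difference.

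**Step 6: counterbalancing.** With six participants per order in each group and sequence in the model, simulation (20,000 replicates) gives an unbiased congruence × time estimate. Type I error is 0.048 to 0.051 for session effects of 0 to 1.0 SD of D. Error df falls from 22 to 21.

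**The case against.** The best defence is that a session effect on the response may be small. Participants have at least five years of resistance training. 1RM was tested 48 hours before the experimental sessions. Tempo, rest and range of motion were controlled. TMG is electrically evoked in a relaxed muscle, which leaves little room for voluntary learning of the outcome. This stands as a reason not to presume a large effect, and it is why the rates above are illustrations, not estimates. It does not break the alias, and it does not rule out a repeated-bout response or residual fatigue in the response at 48 hours.

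Four stronger readings are tempting, but the documents do not support them:

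- A reader might infer that every kind of session effect contaminates the primary test. A shift common to pre and post cancels.
- A reader might infer that assessor blinding is broken because session number reveals congruence. That needs the assessor to know the order rule. Section 3 says the assessor was blinded to "phenotype group and the exercise condition applied (single-blind") and does not say that the rule was known.
- A reader might treat foot-angle × time as the only effect free of a common session effect. Group × Time is free of it too. Foot-angle × time is the only such contrast for the exercise condition.
- A reader might think that randomising the order is a cheap correction now. Section 4.1 gives the achieved sample with its mean age and section 6 reports an observed carry-over result, so the document describes a completed study.

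**Conclusion.** The point holds. Protocol × Time estimates congruence plus any session effect on the pre-to-post response, and no analysis of data collected in this order can separate the two. This follows from the design and needs no numerical assumption. A significant result cannot be attributed to congruence alone, and a null result could reflect opposing effects. Neither the primary nor the secondary hypothesis can be confirmed from this contrast.

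The practical size is unknown. The 6%, 17% and 38% rates depend on assumed session effects of 0.1, 0.3 and 0.5 raw SD and on r = 0.50. They show what an unmodelled session effect could do, not that one occurred. The documents do not show that the findings are wrong, only that this contrast cannot establish their cause.

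**What to change.** 1. In section 3, delete the statement that the fixed order minimises learning effects.
2. In section 6, state that Protocol × Time estimates congruence plus session and cannot be attributed to congruence alone, so the primary and secondary hypotheses cannot be confirmed from it. Say also that the comparison of resting values does not exclude a session effect on the response.
3. Report foot-angle × time (Group × Protocol × Time in section 6's coding) as the one exercise-condition contrast free of a session effect common to both groups, noting that it does not test the congruence hypothesis.
4. Label any within-group analysis of the degree of mismatch as exploratory, with 12 participants per group.

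These are wording and reporting changes. The cost is a weaker conclusion.

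If any data remain to be collected or the study is repeated, randomise order within each phenotype group (six congruent-first, six incongruent-first) and add Session and Session × Time to the model. At the same sample size this costs about one error degree of freedom. For participants already measured it would mean new data collection.

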4. PARTICIPANTS

4.1. Study Population

A total of 24 male athletes (age: 27.5 ± 3.76 years) who were licensed and actively competing in bodybuilding with a minimum of five years of regular resistance training experience volunteered to participate. Prior to the study, participants were provided with detailed information regarding the research protocol and written informed consent was obtained.

4.2. Inclusion Criteria

(a) Aged between 20 and 35 years; (b) a minimum of five years of regular resistance training experience; (c) currently active participation in training; (d) measurements from both feet required to meet the established threshold values for FPA classification.

4.3. Exclusion Criteria

(a) A history of lower extremity surgery or serious musculoskeletal injury within the past year; (b) the presence of congenital or acquired foot deformity; (c) a history of neurological, cardiovascular, or metabolic disease.

4.4. Group Classification

Participants were divided into two groups based on FPA values measured during gait analysis. Participants with a mean FPA exceeding 13° for both feet were classified as the high FPA (HFPA) group ($n=12$), while those with values between 0° and 13° were classified as the normal FPA (NFPA) group ($n=12$). This threshold was established in accordance with reference values recommended in the literature (Cibulka et al., 2016).

4.5. Sample Size Calculation

Sample size was calculated using G*Power 3.1.9.7 software based on a repeated measures mixed-design ANOVA model (within-between interaction). Effect size estimation was based on tensiomyographic changes reported in the lower extremity muscles following acute resistance exercise. Previous studies have reported large effect sizes (Cohen's $d \approx 1.0$ – 1.9) particularly for Tc and Td parameters (Beato et al., 2021). Adopting a more conservative approach, a medium-to-large effect size ($f = 0.40$) was assumed. With a significance level of $\alpha = 0.05$, statistical power of $(1-\beta) = 0.80$, and a correlation between repeated measures of $r = 0.50$, the minimum total sample size was calculated as 20 ($n = 10$ per group). Considering the within-subject comparison advantage of the crossover design and to compensate for potential data loss, 12 participants were included in each group.

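### The minimum sample size of 20 does not follow from its stated inputs, and its effect size describes a change after exercise, not the difference between two changes that the priority test examines

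*Protocol*

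**What the plan says.** Protocol section 4.5 bases the calculation on a "repeated measures mixed-design ANOVA model (within-between interaction") in G*Power 3.1.9.7. The inputs are f = 0.40, α = 0.05, power 0.80 and a correlation of 0.50 between repeated measures. The result is that "the minimum total sample size was calculated as 20", 10 per group, raised to 12 per group. The section states neither the number of repeated measurements entered nor the effect-size option chosen.

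The effect size rests on tensiomyographic changes after acute resistance exercise, with d of about 1.0 to 1.9, "particularly for Tc and Td parameters". The choice of f is introduced as: "Adopting a more conservative approach, a medium-to-large effect size".

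Sections 5.7 and 6 name Dm and Tc as primary and give priority to Protocol × Time. In section 6 Protocol is coded congruent versus incongruent, and both Protocol and Time are within-subject factors. Section 6 also says that partial eta squared is "interpreted as small (0.01), medium (0.06), and large (0.14").

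**The concern.** A sample-size statement should let a reader re-enter the inputs and obtain the same number, and its power should belong to the test on which the conclusion rests. Section 4.5 appears to fail on both counts.

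The second failure matters more. Both foot positions use the same sets, repetitions and load (section 5.6), so each may produce a large change from before to after exercise while the two changes differ little. An effect size taken from the change itself says nothing direct about that difference. If Protocol × Time turns out non-significant, a reader of section 4.5 would take it as a negative result with at least 80% power for a cautiously chosen effect, and the document does not support that.

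**Working it through.** **1. Reproducing the 20.** Inputs from section 4.5: f = 0.40 (f² = 0.16), α = 0.05, power 0.80, r = 0.50, k = 2 equal groups. Sphericity ε = 1, because section 6 applies no correction. The number of measurements m is not stated. The design has 2 protocols × 2 times, so m = 2 (one within factor) and m = 4 (all cells) are both shown as assumptions. Power comes from the noncentral F distribution with df1 = m − 1 and df2 = (N − 2)(m − 1). The noncentrality λ depends on the option:

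- Default: λ = f²·N·m/(1 − r)
- Cohen: λ = f²·N·(m − 1)
- SPSS: λ = f²·(N − 2)(m − 1)

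| Option | m | Smallest even N (power) | Next lower N (power) | Power at 20 | Power at 24 |
|---|---|---|---|---|---|
| Default | 2 | 16 (0.845) | 14 (0.785) | 0.922 | 0.963 |
| Default | 4 | 12 (0.883) | 10 (0.7985) | 0.991 | 0.998 |
| Cohen | 2 | 52 (0.808) | 50 (0.792) | 0.395 | 0.466 |
| Cohen | 4 | 26 (0.834) | 24 (0.798) | 0.707 | 0.798 |
| SPSS | 2 | 54 (0.808) | 52 (0.792) | 0.362 | 0.434 |
| SPSS | 4 | 26 (0.800) | 24 (0.759) | 0.656 | 0.759 |

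Example, default with m = 2 and N = 20: λ = 0.16 × 20 × 2/0.5 = 12.8 on 1 and 18 df, power 0.922. No row gives 20. Among the variants tried, 20 appears only with inputs that section 4.5 does not state or that contradict it, for example r = 0.30 with m = 2, f = 0.35 with m = 2, or a power target of 0.90 with m = 2.

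**2. Which contrast the priority test examines.** Let Δ be the change from before to after exercise, H and N the high- and normal-FPA groups, and 0 and 30 the foot angles. By the secondary hypothesis (section 2.2), the incongruent position is neutral for H and toe-out for N. With 12 per group, congruent minus incongruent change is

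½[(ΔH30 − ΔH0) + (ΔN0 − ΔN30)] = ½[(ΔH30 − ΔH0) − (ΔN30 − ΔN0)].

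The right-hand side is Group × Angle × Time in the angle coding of section 3. The two labels name one contrast, with 1 df on N − 2 = 22 error df. It is a difference between changes. The cited d of 1.0 to 1.9 describes a single change.

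**3. Size of f on the plan's own scale.** Direct conversion: f²/(1 + f²) = 0.16/1.16 = 0.138. The large benchmark of 0.14 corresponds to f = √(0.14/0.86) = 0.403, and the medium benchmark of 0.06 to f = √(0.06/0.94) = 0.253.

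**4. What 24 participants can detect.** Each participant gives D = congruent change − incongruent change, built from four measurements. With a common SD and equal correlation r (assumptions), Var(D) = 4(1 − r) SD², so SE = √[4(1 − r)/24] SD. For 80% power at α = 0.05 on 1 and 22 df, λ = 8.59 and √λ = 2.93. The detectable difference is 2.93 × SE.

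| r | SE (SD) | Detectable difference (SD) | Power for 0.5 SD |
|---|---|---|---|
| 0.50 | 0.289 | 0.85 | 38% |
| 0.70 | 0.224 | 0.66 | 57% |
| 0.80 | 0.183 | 0.54 | 74% |

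**The case against.** **The error is on the safe side.** Under the default option, 20 has 92% power and the enrolled 24 has 96% with m = 2. This stands. A reader might infer from the failed reproduction that the trial is underpowered. The shortfalls in the first table (43% to 47% at 24 with m = 2) need the Cohen or SPSS option, which section 4.5 never says was used, and the η² scale in section 6 is for interpreting results, not for setting the sample size.

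**The wrong test was powered.** A reader might infer this because Protocol × Time is wholly within-subject and section 4.5 names a within-between interaction. The documents do not support it: as shown above, recoding foot angle as congruence turns one into the other, and for an equal standardised contrast the power is the same. What stands is that f was not derived for this contrast.

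**Dm has no basis.** This overreads the text. The word used is particularly, which does not exclude Dm. All that can be said is that no figure for Dm is given.

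**Conservative is a comparative word.** With d = 2f = 0.8, f = 0.40 is indeed below the cited 1.0 to 1.9, and 0.138 is just under 0.14. Both points stand as arithmetic, but the comparison is with a whole change, and a difference between two changes may be much smaller.

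**The sensitivity depends on r.** This stands too. Section 5.3 reports 48-hour test–retest ICCs of 0.91 (Dm) and 0.88 (Tc). Those compare separate measurement occasions without the exercise effect and do not fix the correlation across exercise, but they make 0.50 uncertain. At r = 0.88 the detectable difference would be 0.41 SD, with 92% power for 0.5 SD. A low power for the priority test is therefore not proven; it is left open.

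**Conclusion.** The point holds in two parts. First, 20 is not the minimum that the stated inputs give, under either natural number of measurements or any of the three effect-size options. Second, and more important, the 80% power is not established for the prioritised contrast, because f comes from changes after exercise and not from a difference between two changes. The wording around f = 0.40 adds to the problem: on the plan's own scale it is essentially large.

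This is not a demonstration that 24 participants are too few. Depending on r, they detect a difference of about 0.54 SD (r = 0.80) to 0.85 SD (r = 0.50), assuming a common SD, equal correlations, 80% power, α = 0.05 for each outcome and no missing data. Whether that suffices depends on a plausible size for the difference, which the protocol does not give.

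**What to change.** Rewrite section 4.5 with enrolment unchanged at 24:

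- Correct or remove the 20, and state the number of measurements and the effect-size option entered in G*Power.
- Say that the cited effects are changes after exercise, that no figure is given for Dm, and that they do not estimate the difference between protocols.
- State what 24 participants can detect, for Dm and Tc, as the difference between congruent and incongruent change before to after exercise, over a range of r: 0.85 SD at 0.50, 0.66 SD at 0.70 and 0.54 SD at 0.80 (80% power, α = 0.05, equal correlations, 22 error df).
- Note that this contrast is Protocol × Time in the section 6 coding and Group × Angle × Time in the section 3 coding.
- Drop the description of f = 0.40 as conservative and medium-to-large.

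The cost is one rewritten paragraph and a stated sensitivity that may look less favourable. No participants, measurements or analyses are added.
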